### **10.6.3 Recommendations for managing and monitoring patients reaching LDL-C levels (ie, LDL-C <50 mg/dL [1.30 mmol/L]) during the treatment period**

If a patient achieves a low LDL-C level (ie, LDL-C <50 mg/dL [1.30 mmol/L] on one or more occasion) during the treatment period, then the Investigator will:

- Call the patient/parent as soon as possible to inquire about interval occurrence of AEs.
- Decide whether the patient should be requested to rapidly have an unscheduled site visit, or assessment could be done at the next scheduled visit.
- At the site visit, plan for the following, based on Investigator's medical judgment:
  - Assess the need to have blood drawn from the patient for a repeat lipid assessment in order to confirm the observation of very low LDL-C.
  - Assess the need for conducting clinical investigations, arranging specialist consultation(s) as needed, including with an eye specialist in case of visual problems, as needed, and any relevant additional work-up.
  - Assess the need for alirocumab treatment temporary or permanent discontinuation.

### **10.7 ADVERSE EVENTS MONITORING**

All AEs will be managed and reported in compliance with all applicable regulations, and included in the final clinical study report.

## **11 STATISTICAL CONSIDERATIONS**

### **11.1 DETERMINATION OF SAMPLE SIZE**

No sample size calculation was performed. Eighteen patients are planned to be enrolled to have at least 15 evaluable patients considering the recruitment constraints in this rare disease population.

### **11.2 DISPOSITION OF PATIENTS**

Screened patients are defined as any patient who originally met all the inclusion criteria and none of the exclusion criteria and signed the informed consent.

Enrolled patients consist of all screened patients, with a treatment kit number allocated and recorded in the IVRS/IWRS database, regardless of whether treatment kit was used or not.

### **11.3 ANALYSIS POPULATIONS**

#### **11.3.1 Efficacy population**

The efficacy analysis population will be the ITT population defined as the patients receiving at least one dose or partial dose of IMP.

#### **11.3.2 Safety population**

Safety analyses will be performed on the safety population, which will consist of patients receiving at least one dose or partial dose of IMP.

In addition:

- Patients for whom it is unclear whether they took the study medication will be included in the safety population.

#### **11.3.3 Other analysis populations**

The ADA analysis will be performed on all treated patients (safety population) with a blood sample on Week 0 (baseline) and at least one evaluable blood sample for antibodies post first IMP injection.

The PK analysis will be performed on all treated patients (safety population) with at least one available PK sample post first IMP injection.

## **11.4 STATISTICAL METHODS**

### **11.4.1 Extent of study treatment exposure and compliance**

The extent of study treatment exposure and compliance will be assessed and summarized by dose and overall within the safety population.

#### **11.4.1.1 Extent of investigational medicinal product exposure**

The total exposure will be assessed by:

- Duration of IMP exposure in weeks defined as: (last dose of IMP injection date – first dose of IMP injection date + 14 days)/7, regardless of unplanned intermittent discontinuations.
- The total number of injections by patient.

#### **11.4.1.2 Compliance**

Compliance will be assessed using the following parameters:

- The injection frequency will be defined for each patient as the average number of days between 2 injections, that is: (last dose date – first dose date)/(number of injections -1).

This parameter will be summarized descriptively (N, mean, standard deviation [SD], median, minimum [Min] and maximum [Max]).

### **11.4.2 Analyses of efficacy endpoints**

Efficacy endpoints analyzed with the ITT and on-treatment estimands will be analyzed in the ITT population.

#### **11.4.2.1 Analysis of primary efficacy endpoint(s)**

The percent change from baseline in LDL-C at Week 12 (see [Section 9.1.1](#)) will be analyzed in the ITT population using a mixed-effect model with repeated measures (MMRM) approach. All post-baseline data available within the Week 4 to Week 48 analysis windows will be used and missing data will be accounted for by the MMRM model. The model will include the fixed categorical effect of time point (Weeks 4, 12, 24, and 48), as well as the continuous fixed covariate of baseline LDL-C value.

This model will be run using SAS mixed procedure with an unstructured correlation matrix to model the within-patient errors. Parameters will be estimated using restricted maximum likelihood method with the Newton-Raphson algorithm. Denominator degrees of freedom will be estimated using Satterthwaite's approximation. Throughout the MMRM model, LS mean and standard error (SE) at Week 12 will be provided with the SE and 95% confidence interval (CI).

Robustness of this statistical method will be assessed via sensitivity analysis detailed in the SAP, applying different imputations for missing LDL-C values during the treatment period and missing LDL-C values during the post-treatment period (ie, pattern mixture model).

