Homozygous FH is characterized by drastically increased levels of LDL-C from early childhood onwards. Patients with hoFH have severe hypercholesterolemia (500 to 1000 mg/dL, 12.95 to 25.9 mmol/L), resulting in lifelong exposure to high levels of plasma LDL-C and increased risk of developing atherosclerosis at a highly accelerated rate, often manifesting within the first 2 decades of life. In children, the only clinical symptom is xanthoma tuberosum, typically occurs predominantly on the knees, elbows, and Achilles tendon. If left untreated, it is common that affected subjects die at an early age, due to CVDs (5).

Familial hypercholesterolemia including both heterozygous and homozygous forms may be suspected in a child, adolescent, or young adult (<20 years of age) if he/she has an untreated fasting LDL-C level  $\geq 160$  mg/dL (or non-high density lipoprotein cholesterol [non-HDL-C],  $\geq 190$  mg/dL) (6). Because of the high risk of progression to premature clinical CVD associated with these findings, pediatric guidelines recommend LDL-C lowering intervention and specific lipid targets for children and adolescents with heterozygous familial hypercholesterolemia (heFH). An LDL-C level of <130 mg/dL (3.4 mmol/L) is considered acceptable and <110 mg/dL (2.85 mmol/L) ideal for children with heFH (6), or the achievement of  $\geq 50\%$  reduction in LDL-C. Since LDL-C levels are only indicative of hoFH, especially in children, and do not exclude hoFH diagnosis, a similar LDL-C threshold to that used for heFH will be used to trigger a

genotyping determination. Thus, the protocol will include patients with a screening LDL-C  $\geq 130$  mg/dL (3.4 mmol/L) despite being treated with stable lipid modifying therapy (LMT). The LDL-C targets recommended in the European Atherosclerosis Society (EAS) Consensus Panel statement related to hoFH were  $< 2.5$  mmol/L ( $< 100$  mg/dL),  $< 3.5$  mmol/L ( $< 135$  mg/dL) in children, or  $< 1.8$  mmol/L ( $< 70$  mg/dL) in adults with clinical CVD (2). These targets are similar to those for patients at high cardiovascular risk; however, it is well recognized that these targets are ambitious because they are very difficult to achieve with current lipid modifying treatments.

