## **5 STUDY OBJECTIVES**

### **5.1 PRIMARY**

To evaluate the efficacy of alirocumab (75 or 150 mg depending on BW), administered every 2 weeks (Q2W), on low-density lipoprotein cholesterol (LDL-C) levels at Week 12 of treatment in children with homozygous familial hypercholesterolemia (hoFH) 8 to 17 years of age on top of background treatments.

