### 7.2.1 Exclusion criteria related to study methodology

E 01. Children and adolescents aged less than 8 years or more than 17 years at the time of informed consent signature, unless different local regulation applies (eg, for Russia only: patients aged less than 12 years or more than 17 years at the time of informed consent signature).

*Note: Patients aged 8 to less than 10 years who have not had previous attempts to lower LDL-C by other means will be excluded.*

E 02. Patients with LDL-C (pre-apheresis, if applicable) less than 130 mg/dL (3.37 mmol/L) obtained during the screening period after the patient has been on stable apheresis procedure or LMT (ie, stable optimal dose of statin ± other stable LMTs, or stable non-statin LMTs in statin-intolerant patients) treatment for at least 4 weeks.

E 03. Patients with null LDLR mutations in both alleles.

E 04. Patients with BW less than 25 kg.

E 05. Patients aged 8 to 9 years not at Tanner Stage 1 and patients aged of 10 to 17 years not at least at Tanner Stage 2 in their development (See [Appendix C](#)).

E 06. Daily dose of statin that is above the maximum recommended dose for pediatric patients as per the local prescribing label.

E 07. Patients who will receive statin de novo during the run-in period.

E 08. Use of nutraceutical products or over-the-counter therapies that may affect lipids which have not been at a stable dose for at least 4 weeks prior to the screening visit.

E 09. Patients not previously instructed on a cholesterol-lowering diet prior to the screening visit.

E 10. Mipomersen in the last 5 months.

E 11. Patients with uncontrolled (ie, hemoglobin A1c [HbA1c] >9% at the screening visit) Type 1 or 2 diabetes mellitus.

E 12. Patients with known uncontrolled thyroid disease (ie, thyroid-stimulating hormone levels outside of the laboratory's reference range within the past 6 months, or with elevated free T3 or T4 and with clinical symptoms of hyperthyroidism).

E 13. Patients who use systemic corticosteroids.

*Note: Topical, intra-articular, nasal, inhaled, and ophthalmic steroid therapies are not considered as 'systemic' and are allowed.*

E 14. Patients with uncontrolled (ie, systolic blood pressure [SBP] or diastolic blood pressure [DBP] above local guidelines or equivalent) hypertension.

E 15. Fasting triglycerides >350 mg/dL (3.95 mmol/L) at the screening visit.

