#### **8.4 METHOD OF ASSIGNING PATIENTS TO TREATMENT GROUP**

This is an open-label study and every patient will receive alirocumab.

The lists of treatment kit numbers will be generated centrally by sanofi. The IMPs will be packaged in accordance with those lists.

The Trial Supply Operations Manager (TSOM) will provide the list of treatment kit numbers. Then, this centralized treatment allocation system provider will generate the patient list and allocate the treatment kits to the patients.

Before allocating a treatment kit to the patient, the Investigator or designee will have to contact the centralized treatment allocation system.

Two types of centralized treatment allocation system will be used, the Interactive Voice Response System (IVRS) and the Interactive Web Response System (IWRS) depending on the choice of the site. Interactive response technology (IRT) covers both centralized treatment allocation.

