### **9.2 SECONDARY ENDPOINTS**

#### **9.2.1 Secondary efficacy endpoints**

- Percent change in LDL-C (pre-apheresis, if applicable) from baseline to Week 12 in the ITT population, using all LDL-C values during the treatment period (on-treatment estimand).
- Percent change in LDL-C (pre-apheresis, if applicable) from baseline to Weeks 24 and 48 (ITT and on-treatment estimands).
- Percent change in Apo B, non-HDL-C, Total-C, Lp (a), HDL-C, fasting TG and Apo A-1 (pre-apheresis, if applicable) from baseline to Weeks 12, 24, and 48 (ITT and on-treatment estimands).
- Proportion of patients with  $\geq 15\%$  reduction in LDL-C (pre-apheresis, if applicable) at Weeks 12, 24, and 48 (ITT and on-treatment estimands).
- The absolute change in LDL-C from baseline to Weeks 12, 24, and 48 (ITT and on-treatment estimands).

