##### Continuous endpoints anticipated to have a normal distribution

Continuous secondary efficacy endpoints analyzed with the ITT estimand and anticipated to have a normal distribution (ie, lipids other than TG and Lp (a)) will be analyzed using the same MMRM model as for the primary endpoint with the corresponding baseline and post-baseline values.

Continuous secondary efficacy endpoints analyzed with the on-treatment estimand and anticipated to have a normal distribution will be analyzed using the same MMRM model but only including on-treatment values. The treatment period is defined as the time period from the first IMP injection up to the day of last injection + 21 days.

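### The single-arm MMRM confidence interval leaves out the sampling error of mean baseline LDL-C, so it is too narrow for the population mean wherever change depends on baseline

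*Protocol*

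**What the plan says.** Protocol section 11.4.2.1 specifies the primary analysis closely. It is an MMRM on percent change in LDL-C, with time point (Weeks 4, 12, 24 and 48) "as well as the continuous fixed covariate of baseline LDL-C value". It is run in the SAS mixed procedure with unstructured covariance, REML and Satterthwaite degrees of freedom. The output is also fixed: "LS mean and standard error (SE) at Week 12 will be provided with the SE and 95% confidence interval (CI". For this model, what the section leaves to the SAP is the sensitivity analysis for missing values.

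Under section 11.4.2.2, the continuous secondary lipid endpoints expected to be normal "will be analyzed using the same MMRM model as for the primary endpoint". That takes in absolute LDL-C change at Weeks 12, 24 and 48, listed in section 9.2.1.

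There is one arm (section 8.4): "This is an open-label study and every patient will receive alirocumab". The primary objective (section 5.1) concerns the effect "at Week 12 of treatment in children with homozygous familial hypercholesterolemia (hoFH) 8 to 17 years of age", which describes a population of patients. Section 11.1 says that no sample size calculation was done and plans 18 enrolled for at least 15 evaluable.

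**The concern.** An LS mean from this model is, by software default, taken at the average baseline of the patients in the data set. Its SE contains only the residual variance, that is, the scatter left after regression on baseline. Another sample of 15 to 18 children would have a different average baseline and, if change depends on baseline, a different average change. That part of the uncertainty is left out. In a randomised comparison it would largely cancel between arms. Here there is nothing to cancel it against.

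The two LDL-C endpoints cannot both escape. Absolute change equals baseline times percent change. If mean percent change is unrelated to baseline, mean absolute change is proportional to baseline. If the mg/dL reduction is constant, percent change varies as 1/baseline. With a non-zero mean effect and a monotone relation, the two slopes cannot both be zero. The protocol does not show which pattern holds.

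The study has no hypothesis test and no sample size calculation, so this interval is its only stated measure of precision. The risk is overstated precision when the interval is read as applying to paediatric hoFH.

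**Working it through.** **The plan's own figures.** There is no SE, interval width or power to reproduce. Going from 18 to 15 implies only 1 - 15/18 = 16.7% non-evaluable.

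**Formula.** With complete data, the Week 12 LS mean at the sample mean baseline equals the raw Week 12 mean. Then:

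- model variance = residual variance / n
- variance for the population mean = (residual variance + slope² × Var(baseline)) / n
- ratio of the two SEs = sqrt(1 - R²), with R² the squared correlation of change with baseline

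Approximate coverage of a nominal 95% interval at n = 18 under normality:

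| R² | SE ratio | Coverage |
|---|---|---|
| 0 | 1.00 | 95.0% |
| 0.10 | 0.95 | 93.9% |
| 0.20 | 0.89 | 92.4% |
| 0.30 | 0.84 | 90.5% |

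**Inputs from the protocol.**

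- Mean percent change -24% (section 4: LDLR-defective patients on another PCSK9 inhibitor).
- Entry floor of 130 mg/dL (section 7.2.1, E 02): "Patients with LDL-C (pre-apheresis, if applicable) less than 130 mg/dL (3.37 mmol/L) obtained during the screening period" are excluded. The criterion sets no upper limit.
- Typical hoFH levels of 500 to 1000 mg/dL (section 4).

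**Assumptions.**

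- SD of percent change 15, 20 or 25 points.
- Baseline flat over 130 to 1000 mg/dL: mean 565, variance 870²/12 = 63,075, SD 251, CV 0.44.
- Or flat over 500 to 1000 mg/dL: CV 0.19.

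**Absolute change, percent change unrelated to baseline (wide span, SD 20, n = 18).**

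- Slope part: 0.24² × 63,075 = 3,633.
- Residual part: 0.20² × (565² + 63,075) = 0.04 × 382,300 = 15,292.
- R² = 3,633 / 18,925 = 0.19.
- Model SE = sqrt(15,292/18) = 29.1 mg/dL. Population SE = sqrt(18,925/18) = 32.4 mg/dL.
- With t = 2.120, the half-width is 61.8 mg/dL where 68.7 is needed.

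The same formula gives R² = 0.30 at SD 15 and 0.13 at SD 25.

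**Percent change, constant mg/dL reduction (wide span, SD 20 about the curve, n = 18).**

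- Mean of 1/baseline = ln(1000/130)/870 = 0.002345, so an average of -24% means a reduction of 0.24/0.002345 = 102 mg/dL.
- The fitted line explains 175 of a total variance of 630 (230 from the curve plus 20² = 400), so R² = 0.28.
- Model SE = sqrt(455/18) = 5.0 points. Population SE = sqrt(630/18) = 5.9 points.

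**Simulated coverage of the population mean.** REML MMRM with four visits, unstructured covariance, complete data and visit correlation 0.7. Main wide-span cells used 24,000 to 36,000 trials (Monte Carlo error about 0.2 points). Paired entries are n = 15 / n = 18.

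| Baseline span | Pattern | Endpoint | SD 15 | SD 20 | SD 25 |
|---|---|---|---|---|---|
| 130–1000 | % change unrelated to baseline | Absolute | 89.3 / 89.2 | 91.4 / 91.4 | 92.4 / 92.3 |
| 130–1000 | Constant mg/dL reduction | Percent (primary) | 88.5 / 88.2 | 90.8 / 91.0 | 92.2 / 92.4 |
| 130–1000 | Constant mg/dL reduction | Absolute | about 94 over the range | | |
| 130–1000 | % change ∝ 1/sqrt(baseline) | Percent | 92.9 to 94.5 over the range | | |
| 130–1000 | % change ∝ 1/sqrt(baseline) | Absolute | 93.3 to 94.2 over the range | | |
| 500–1000 | Either extreme (R² 0.03 to 0.09) | The affected one | 93.6 to 94.9 over the range | | |

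If percent change is unrelated to baseline, the primary interval covers about 95% as planned.

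**Is it the baseline term or non-normality?** A plain t-interval on the same absolute-change data (wide span, percent change unrelated to baseline) covers 93.9 to 94.4%. So 2.0 to 4.9 points of the shortfall come from fixing baseline, and 0.6 to 1.1 from non-normality.

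**Missing data.** With 18 enrolled and 3 missing from Week 12 on (3,000 trials, wide span, SD 15/20/25), absolute change covers 88.8/91.2/92.4%. Percent change under a constant reduction covers 89.4/91.7/92.5%. Bias is at most 0.42 mg/dL or 0.22 points.

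**After adding slope² × Var(baseline)/n.** Coverage in the main complete-data cells is 94.6 to 95.7%. With missing data it is 94.4 to 94.9% (absolute) and 95.6 to 96.1% (percent).

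**The case against.** The strongest reply is that nothing is stated wrongly. A covariate-adjusted LS mean with a model-based SE is a standard conditional estimate, valid at the observed average baseline, and the reference value of a covariate is often left to the SAP. It is true that the protocol does not name the baseline value, and that the sample mean is inferred from the software default. But section 11.4.2.1 fixes the model, procedure, degrees of freedom and reported interval, so the default interval follows from the protocol. The objective it serves is about children with hoFH, not about the average baseline of those enrolled.

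Second, the size rests on assumptions. Neither the baseline SD nor the SD of change is given. The 130 to 1000 mg/dL span joins an on-treatment entry floor to the top of a general disease range, and the lowest coverage needs an extreme pattern at the smallest SD. That stands, and it is why the result is a range. Narrower spans reduce the shortfall without removing it: 130 to 600 and 300 to 1000 mg/dL give about 91 to 93.5% for absolute change.

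Third, for the primary endpoint the loss is hypothetical, since no R² is given, and no threshold depends on the interval. Both points stand.

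Fourth, the added term uses a squared estimated slope, so it errs slightly wide. That stands too, at the cost given under the fix.

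**Conclusion.** The concern holds. Read as an interval for the mean in paediatric hoFH, the planned CI is too narrow by the factor sqrt(1 - R²). For absolute LDL-C change this is expected unless percent change falls in inverse proportion to baseline. For the primary percent change it is conditional: negligible up to R² of about 0.04, about one point of coverage at 0.1, and material from about 0.2.

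Over the assumed 130 to 1000 mg/dL span and SDs of 15 to 25 points, the affected endpoint loses about 3 to 7 points of coverage in the two extreme patterns, and less in between. Over 500 to 1000 mg/dL the loss is at most about 1.5 points. The condition is a non-zero linear slope on baseline. Curvature with no linear slope stays in the residual variance and does no harm. The complete-data point estimate is unaffected, and the interval remains valid conditional on the observed average baseline.

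**What to change.** Keep the baseline-adjusted MMRM. In section 11.4.2.1, state that the Week 12 LS mean is taken at the mean baseline of the patients in the model, and that it is meant for the population in the primary objective. Compute the CI from

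SE² = SE_model² + slope² × s²_baseline / n,

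with n all patients in the model and the model's own Satterthwaite degrees of freedom for the LS mean. In complete-data checks these averaged 13.0 at n = 15 and 15.9 at n = 18. Apply this at least to absolute LDL-C change, and to the primary and the other MMRM endpoints for consistency.

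The cost is one variance term per estimate. Intervals widen by 3 to 4% where baseline has no effect, with coverage up to about 96%. In the wide-span cases they widen by 11 to 23% for absolute change and 15 to 31% for percent change; a second simulation gave 12 to 27% and 16 to 33%. In the narrow span at SD 15 they widen by 7 to 9%.

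Two limits apply. With a strongly skewed baseline the corrected interval can still fall a little short: an assumed lognormal baseline with CV 0.60, SD 15 and n = 18 gives 83.6% as planned and 93.2% corrected for absolute change. A percentile bootstrap is no substitute at this sample size, as it covers only 90.2 to 91.7%.

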#### **11.4.2.2 Analyses of secondary efficacy endpoints**

Multiple types of measurements are planned to be analyzed (see [Section 9.2](#)) during differing time points in the trial, specifically continuous measurements expected to have a normal distribution (eg, percent change in LDL-C), continuous measurements expected to have a non-normal distribution (eg, TG), and binary measurements (eg, proportion of patients with  $\geq 15\%$  reduction in LDL-C).

##### Continuous endpoints anticipated to have a normal distribution

Continuous secondary efficacy endpoints analyzed with the ITT estimand and anticipated to have a normal distribution (ie, lipids other than TG and Lp (a)) will be analyzed using the same MMRM model as for the primary endpoint with the corresponding baseline and post-baseline values.

Continuous secondary efficacy endpoints analyzed with the on-treatment estimand and anticipated to have a normal distribution will be analyzed using the same MMRM model but only including on-treatment values. The treatment period is defined as the time period from the first IMP injection up to the day of last injection + 21 days.

